# 1. INTRODUCTION

Basal cell carcinoma (BCCA) is the most common human cancer, and frequently affects facial structures. While rarely fatal, facial BCCA can be disfiguring and expensive to treat. Treatment of facial BCCA typically includes Mohs micrographic surgery followed by plastic reconstructive surgery. Success rates of treatment for non-metastatic BCCA that is limited to skin can approach 99%. However, deeply invasive BCCA can involve vital organs, such as the eye or lacrimal drainage system, requiring aggressive surgical interventions that often compromise organ function. Hence, there is a critical need for improved treatments of invasive BCCA in the face.

Vismodegib is a small, orally administrable molecule that functions as an antagonist of the smoothed receptor (SMO), which is part of the hedgehog signaling pathway. Vismodegib (Erivedge, Genentech), was recently approved by the Food and Drug Administration (FDA) for treatment of recurrent, locally advanced or metastatic BCCA. Its primary indication in these cases is organ preservation. Initial results from clinical usage have been very promising. However, it remains to be determined whether use of vismodegib in treating locally advanced periocular or orbital BCCA would increase the chance of preserving visual function. Furthermore, chronic use of vismodegib is associated with side effects, such as muscle spasms, weight loss, hair loss, fatigue, and loss of appetite. Some side effects, such as muscle spasms, can be functionally debilitating. Recent reports have suggested that vismodegib treatment for orbital BCCA may facilitate globe preservation even if surgery is eventually required (Kahana, Worden and Elner, JAMA Ophthalmol, 2013). **The goal of this study is to test whether treatment with vismodegib for periocular and orbital BCCA is associated with preservation of a functioning globe and lacrimal apparatus.** Recruitment will be limited to patients who meet the standard criteria for vismodegib treatment of locally advanced periocular/orbital BCCA, for whom vismodegib has the potential to be organ-preserving.

## 1.1 Disease Background

### Background on Basal Cell Carcinoma

Basal cell carcinoma (BCC) is the most common human cancer, affecting approximately 750,000 Americans per year (Epstein 2008). Based on rapidly rising tumor incidence rates, it is estimated that almost 1 in 3 Caucasians born in the United States after 1994 will develop a BCC during their lifetime (Miller and Weinstock 1994). Like other skin cancers, BCC risk is correlated inversely with the degree of skin pigmentation and positively with exposure to ultraviolet or ionizing radiation. In states near

the equator, such as Hawaii, BCC incidence is approaching 3-fold that of states in the Midwest, such as Minnesota.

BCC incidence also varies globally. The highest rates of skin cancer occur in South Africa and Australia, areas that receive high amounts of UV radiation (Marks et al. 1989). Australia has a trend toward increasing BCC incidence, whereas Finland has a low reported incidence that is approximately one quarter that in Minnesota; nonetheless, BCC incidence in Finland appears to be increasing, especially among young women. A study from the Netherlands found that high socioeconomic status was associated with increased incidence of BCC among men, suggesting that BCC is changing from a disease of the poor to a disease of the rich, at least in northern Europe (van Hattem et al. 2009).

BCCs are generally treated by local excision, which in many cases is associated with scarring and potential disfigurement. Until recently, there has been no reliable medical (non-surgical) therapy for BCC, particularly for advanced forms of the disease.

## 1.2 The Hedgehog Signaling Pathway and Basal Cell Carcinoma Pathogenesis

The vast majority of cases of BCC occur sporadically. However, a rare autosomal dominant inherited condition has been identified – Gorlin syndrome (also known as basal cell nevus syndrome [BCNS] or nevoid basal cell carcinoma syndrome) – in which individuals develop many BCCs (tens to thousands) from a relatively early age (Gorlin 1987; Online Mendelian Inheritance in Man 2012). The mutant gene in Gorlin syndrome has been mapped using genetic linkage studies to human chromosome 9q22 and, subsequently, to the Patched 1 (PTCH1) gene (Gailani et al. 1992; Hahn et al. 1996). PTCH1 is a member of the Hedgehog (Hh) signaling pathway, a critical regulator of both cellular growth and differentiation during embryonic development (Caro and Low 2010).

The Hh pathway operates in both time- and position-dependent mechanisms to allow developing tissues to attain their correct size, location, and cellular content (Caro and Low 2010). The pathway was originally identified in the fruit fly *Drosophila melanogaster*, where mutations in the Hh gene gave rise to embryos covered in spiky processes, suggesting the “hedgehog” name. In fruit flies, as well as humans, signaling in the pathway is initiated by the hydrophobic secreted Hh protein, which binds to PTCH1, a 12-transmembrane domain protein located on the cell membrane. This binding releases inhibition of the Smoothed (SMO) protein, a 7-transmembrane G-protein-coupled-like receptor located on the membrane of intracellular endosomes. Activated SMO, in turn, transmits a signal via interacting proteins, leading to

activation of the Gli family of zinc finger transcription factors. In patients with Gorlin syndrome, loss of function of PTCH1 constitutively turns on the Hh pathway by allowing SMO to constitutively activate its downstream targets, thereby leading to the high incidence of BCCs.

Subsequent studies have shown that approximately 90% of sporadic BCCs also have *de novo* mutations in PTCH1, whereas the remaining 10% have activating mutations in SMO that prevent inhibition by normal PTCH1 protein (Epstein 2008; Scales and de Sauvage 2009). Thus, a common genetic basis exists for the sporadic and syndrome-associated forms of BCC, suggesting both may be amenable to treatment with inhibitors of the Hh pathway.

The feasibility of blocking Hh signaling *in vivo* was first demonstrated in studies of teratogenic phenomena that were observed in lambs born of ewes that had ingested the forage plant, *Veratrum californicum* (Binns et al. 1963). The active agent in the plant was shown to be cyclopamine, a steroidal alkaloid that induces midline deformities, including cyclopia, which blocks SMO signaling in the developing lamb fetus (Chen et al. 2002).

Cyclopamine has proven to be a valuable tool to confirm the importance of Hh signaling in a subset of malignancies. One study, for instance, showed that chronic oral administration of cyclopamine reduced the development of UVB-induced BCCs in the skin of *Ptch1* (+/-) mice, an animal model for Gorlin syndrome, by approximately 67% (Athar et al. 2004). Another study found that 25% of small-cell lung cancers expressed elevated levels of Hh ligand and *GLI1* and that cyclopamine inhibited the growth of SCLC cell lines in culture (Watkins et al. 2003). Similarly, systemic cyclopamine treatment slowed the growth of pancreatic cancer xenografts and blocked the metastatic potential of prostate cancer cells in mice (Thayer et al. 2003; Karhadkar et al. 2004). Finally, activation of Hh signaling in some types of extracutaneous tumors has been shown to be due to tumor cell expression and secretion of Hh ligand and subsequent activation of the pathway in stromal cells, which leads to secondary growth stimulation of the tumor cells by stromally-expressed cytokines (Yauch et al. 2008).

### **1.3 Clinical Experience, Vismodegib Safety and Efficacy**

#### **Background on Vismodegib**

Vismodegib is a small molecule inhibitor of SMO developed by Genentech, Inc. for the treatment of tumors in which the Hh signaling pathway appears to contribute to the development and maintenance of tumorigenesis. Vismodegib, a systemic Hh pathway antagonist, has been shown to have oral bioavailability and potent anti-tumor activity in a variety of primary human tumor xenografts and tumor cell line xenograft models

(see the Vismodegib Investigator Brochure and the US package insert for further details).

### 1.3.1 Malignancies with Mutation Driven Hh Pathway Signaling

#### 1.3.1.1 Basal Cell Carcinoma

##### Phase I Study SHH3925g - Safety and Pharmacokinetics Assessment

A Phase I, company-sponsored clinical trial (SHH3925g) assessed the safety and pharmacokinetics (PK) of vismodegib and responses of metastatic or locally advanced BCC to the drug (Von Hoff et al. 2009). Thirty-three patients with metastatic or locally advanced BCC received oral vismodegib at one of three doses: 17 patients received 150 mg per day, 15 patients received 270 mg per day, and 1 patient received 540 mg per day (median duration of treatment was 9.8 months). Of the 33 patients, 18 had an objective response to vismodegib, according to assessment on imaging (7 patients), physical examination (10 patients), or both (1 patient). Of the patients who had a response (see Table 1), 2 had complete responses (CRs) and 16 had partial responses (PRs). The other 15 patients had either stable disease (11 patients) or progressive disease (4 patients). Eight Grade 3 adverse events (AEs) that were deemed to be possibly related to the study drug were reported in 6 patients (see Table 2), including fatigue (4 AEs), hyponatremia (2 AEs), muscle spasm (1 AE), and atrial fibrillation (1 AE). One patient withdrew from the study because of AEs.

**Table 1: SHH3925g Phase I Efficacy Results**

	aBCC (n=33)
Objective response, n (%)	18 (54.5%)
Complete response, n (%)	2 ( 6.1%)
Partial response, n (%)	16 (48.5%)
Stable disease, n (%)	11 (33.3%)
Progressive disease, n (%)	4 (12.1%)

**Table 2: SHH3925g Phase I Adverse Events in Patients With aBCC (n=33)**

Clinical Event	Grade 2	Grade 3	Grade 4
	Number of Patients With Event		
Fatigue	0	4	0
Hyponatremia	0	2	1
Muscle spasm	3	1	0
Atrial fibrillation	0	1	0
Dysgeusia	2	n/a	n/a
Anorexia	2	0	0
Weight loss	2	2	0
Dyspepsia	1	0	0
Dyspnea	0	2	0
Aspiration	0	1	0
Back pain	0	1	0
Corneal abrasion	0	1	0
Dehydration	0	1	0
Keratitis	0	1	0
Lymphopenia	0	1	0
Pneumonia	0	1	0
Urinary tract infection	0	1	0
Electrocardiographic event (prolonged QT interval)	0	1	0

### **Phase II Study ERIVANCE (SHH4476g) in Metastatic and Locally Advanced Basal Cell Carcinoma**

A multicenter, international, two-cohort, nonrandomized, pivotal, Phase II, company-sponsored study (SHH4476g) enrolled patients with metastatic BCC and those with locally advanced BCC who had inoperable disease or for whom surgery was inappropriate (because of multiple recurrences and a low likelihood of surgical cure, or substantial anticipated disfigurement) (Sekulic et al. 2012). In 33 patients with metastatic BCC (see Table 3), the independently assessed response rate was 30% (95% confidence interval [CI], 16 to 48;  $p=0.001$ ). In 63 patients with locally advanced BCC (see Table 4), the independently assessed response rate was 43% (95% CI, 31 to 56;  $p<0.001$ ), with complete responses in 13 patients (21%). The median duration of response was 7.6 months in both cohorts at the time of data cutoff. Muscle spasms, alopecia, dysgeusia, weight loss, and fatigue occurred in more than 30% of patients, whereas serious adverse events

(SAEs) were reported in 25% of patients. Seven deaths due to AEs were reported and none of the deaths were related to vismodegib.

Based on the results of this pivotal trial, vismodegib was approved on January 30, 2012 by the United States Food and Drug Administration (US FDA) for the treatment of adults with metastatic basal cell carcinoma, or with locally advanced basal cell carcinoma that has recurred following surgery or who are not candidates for surgery, and who are not candidates for radiation. (Erivedge [package insert] 2013).

**Table 3: Efficacy Results from Primary Analysis**

	Metastatic BCC (n=33)		Locally Advanced BCC (n=63)	
	IRF (1°)	INV (2°)	IRF (1°)	INV (2°)
Response ORR	10 (30%)	15 (45%)	27 (43%)	38 (60%)
95% CI	(16%, 48%)	(28%, 62%)	(30%, 56%)	(47%, 72%)
P value	0.001		<0.001	
SD	21 (64%)	15 (45%)	24 (38%)	15 (24%)
PD	1 (3%)	2 (6%)	8 (13%)	6 (10%)
Unevaluable/ missing	1 (3%)	1 (3%)	4 (6%)	4 (6%)
Median DoR, mos	7.6	12.9	7.6	7.6

**Table 4: ERIVANCE Investigator Assessed Efficacy at the18-Month Update**

Investigator Assessed (INV)	mBCC (n = 33)	laBCC (n = 63)	Total (n = 96)
ORR, n (%) [95% CI]	16 (48.5) [30.8-66.2]	38 (60.3) [47.2-71.7]	54 (56.3) [45.7-66.4]
Complete response	0	20	20
Partial response	16	18	34
Stable disease	14	15	29
Progressive disease	2	6	8
Median duration of response, months, (95% CI)	(n = 16) 14.7 (5.6-17.0)	(n = 38) 20.3 (9.0-NE)	(n = 54) 16.8 (9.5-NE)
Median PFS, months, (95% CI)	9.3 (7.4-16.6)	12.9 (10.2-31.4)	12.8 (9.5-18.0)
Median OS, months, (95% CI)	30.9 (18.1-NE)	NE (NE-NE)	NE (NE-NE)
1-Year survival rate, % (95% CI)	78.7 (64.7-92.7)	93.1 (86.6-99.6)	NA

**Table 5: ERIVANCE Safety Results at the 18-Month Update**

	Metastatic BCC (n = 33)	Locally Advanced BCC (n = 71)
All AE	33 (100%)	71 (100%)
Grade 3-5 Adverse Event	14 (42.4%)	40 (56.4%)
Grade 5 Adverse Event§	1 (3%)	6 (8.5%)
Serious Adverse Events	8 (24.2%)	28 (39.4%)
Adv. Events Leading To Treatment Discontinuation	5 (15.2%)	16 (22.5%)

§ No new deaths on study since the primary data analysis. Fatal events included: Death of unknown cause (n=3), acute myocardial infarction (n=1), ischemic stroke (n=1), meningeal disorder (n=1), and hypovolemic shock (n=1). In all cases, clinically significant risk factors or comorbid conditions were present at baseline. Relationship between study drug and event is unknown.

**Table 6: Most Frequent Treatment Emergent Adverse Events (>10% of patients) at the 18-Month Update**

Adverse Event, n (%)	NCI CTCAE Grade, (N = 104)					
	Total	1	2	3	4	5
Any adverse events	104 (100.0)	11 (10.6)	38 (36.5)	34 (32.7)	13 (12.5)	7 (6.7)
Muscle spasms	74 (71.2)	49 (47.1)	19 (18.3)	6 (5.8)	0	0
Alopecia	68 (65.4)	48 (46.2)	20 (19.2)	n/a	n/a	n/a
Dysgeusia	57 (54.8)	31 (29.8)	26 (25.0)	n/a	n/a	n/a
Weight decreased	53 (51.0)	29 (27.9)	17 (16.3)	7 (6.7)	n/a	n/a
Fatigue	44 (42.3)	32 (30.8)	7 (6.7)	4 (3.8)	1 (1.0)	0
Nausea	34 (32.7)	25 (24.0)	9 (8.7)	0	0	0
Decreased appetite	28 (26.9)	18 (17.3)	7 (6.7)	3 (2.9)	0	0
Diarrhea	28 (26.9)	20 (19.2)	5 (4.8)	3 (2.9)	0	0
Constipation	20 (19.2)	14 (13.5)	6 (5.8)	0	0	0
Cough	20 (19.2)	16 (15.4)	4 (3.8)	0	0	0
Vomiting	18 (17.3)	15 (14.4)	3 (2.9)	0	0	0

Adverse Event, n (%)	NCI CTCAE Grade, (N = 104)					
	Total	1	2	3	4	5
Arthralgia	17 (16.3)	12 (11.5)	4 (3.8)	1 (1.0)	0	0
Headache	15 (14.4)	12 (11.5)	3 (2.9)	0	0	0
Nasopharyngitis	13 (12.5)	11 (10.6)	2 (1.9)	0	0	0
Squamous cell carcinoma	12 (11.5)	3 (2.9)	5 (4.8)	3 (2.9)	0	0
Ageusia	12 (11.5)	8 (7.7)	4 (3.8)	n/a	n/a	n/a
Hypogeusia	11 (10.6)	10 (9.6)	1 (1.0)	n/a	n/a	n/a

### Expanded Access Study (SHH4811g) in Advanced BCC

An open-label, single-arm, multicenter, expanded access study (SHH4811g) of an oral repeating dose of vismodegib was conducted in patients with locally advanced or metastatic BCC, who are otherwise without satisfactory treatment options. Safety of vismodegib and objective response in patients with measurable disease (RECIST v1.0) were assessed (Weiss G, et al. Poster, ESMO 2012). The study has been completed following FDA approval and commercial availability of vismodegib.

Among 95 efficacy evaluable patients (56 patients with laBCC and 39 patients with mBCC) at the time of final analysis data cutoff date of 23 April 2012 the observed objective response rates (see Table 7) were 46.4% (95% CI, 33.0%, 60.3%) for patients with laBCC (n = 56) and 30.8% (95% CI, 17.0%, 47.6%) for patients with mBCC (n = 39). Complete response, partial response and stable disease were observed in 10.7%, 35.7%, and 48.2%, respectively, of patients with laBCC; no patients in this cohort exhibited PD as best response. For patients with mBCC, complete response, partial response and stable disease rates observed were 5.1%, 25.6%, and 51.3%, respectively. 7.7% of patients in this cohort exhibited PD as best response. Among patients with laBCC who responded the median and mean times to response were 2.6 months and 3.5 months, respectively; and among patients with mBCC who responded the median and mean times to response were 2.6 months and 3.8 months, respectively.

As of the final analysis data cutoff date of 23 April 2012, 116 of 119 safety evaluable patients (97.5%) experienced at least one adverse event (22 SAEs total, see Table 8). Adverse events that had the highest reported occurrences ( $\geq$  20%) in 119 safety evaluable patients were: muscle spasms (84 patients; 70.6%), dysgeusia (84 patients; 70.6%), alopecia (69 patients; 58.0%), and diarrhea (30 patients; 25.2%). Only one of 22 SAEs (4.5%) was assessed as being related to treatment with vismodegib: a Grade 3 muscle spasm, reported

in 1 patient. There have been three deaths among 119 safety-evaluable patients (2.5%); 2 assessed as unrelated to study drug, and 1 patient with PD.

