## Phase II BCNS Study (SHH4685s)

The anti-BCC efficacy of vismodegib was tested in a randomized, double-blinded, placebo-controlled, Investigator-sponsored trial in Gorlin syndrome (BCNS) patients with surgically eligible BCCs (Tang et al. 2012). Forty-one patients were randomized 2:1 to receive oral vismodegib (n=26) or placebo (n=15). After a mean follow up of 8 months (range, 1 to 15 months), the per-patient rate of new surgically eligible BCCs (SEBs) was lower with vismodegib than with placebo (2 vs. 29 cases per group per year,  $p<0.001$ ), as was the size (percent change from baseline in the sum of the longest diameter) of existing clinically significant BCCs ( $-65\%$  vs.  $-11\%$ ,  $p=0.003$ ). In some patients, all BCCs clinically regressed. No tumors progressed during treatment with vismodegib. Patients receiving vismodegib routinely had Grade 1 or 2 AEs of loss of taste, muscle cramps, hair loss, and weight loss. Overall, 54% of patients (14 of 26) receiving vismodegib discontinued drug treatment due to AEs. At 1 month, vismodegib use had reduced the Hh pathway's target-gene expression in BCC cells by 90% ( $p<0.001$ ) and diminished tumor-cell proliferation, but apoptosis was not affected. No residual BCC was detectable in 83% of biopsy samples taken from sites of clinically regressed BCCs. At the second pre-specified interim analysis, a data safety and monitoring board concluded that the pre-determined threshold for a significant difference between the two groups had been reached ( $p<0.0113$ ), and the treatment with placebo in this arm was terminated. See the Vismodegib Investigator Brochure and the US package insert for additional details on nonclinical and clinical studies on vismodegib.

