## **RESPONSE ASSESSMENT**

- 5) Assess response by ophthalmic exam at 3 month intervals or at time of early discontinuation of vismodegib (by treating physician or qualified designee), + MRI or CT with contrast at 5 and once in the timeframe from 9-12 months (+/- 1 month) and clinical photography.
- 6) Treatment response will be determined per Response Evaluation Criteria in Solid Tumors (**RECIST**) protocol, using clinical measurements and/or tumor imaging measurements (determined by treating physician):
  - i. Complete response (CR) = complete disappearance of tumor
  - ii. Partial response (PR) = at least 30% decrease in largest diameter
  - iii. Progressive disease (PD) = at least 20% increase in largest diameter
  - iv. Stable disease (SD) = neither PR nor PD
- 7) Determination of whether the tumor is progressing (PD) vs. responding (SD, PR or CR) will be done at regular intervals (3 months), until 1 year after initiation of vismodegib treatment. Following the 1 year mark, patients will continue to be followed per SOC.

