### Analysis

Treatment outcome (Visual Function Score; Table 15) will be measured overall (primary endpoint). The **primary** outcome will be the assessment of the visual system using a weighted assessment scale per Table 15. A weighted score of 21 or more (out of possible 50) constitutes a successful outcome.

Exact binomial one-sided tests will be used to compare success rate of the primary outcome (Visual Function Score, Table 15) to 30% (a literature- and practice-based estimate of the loss of visual and lacrimal function after treatment of locally advanced periocular/orbital BCCA). If the true success rate is 50%, the study will have 90% power to reject the null hypothesis ( $p=0.3$ ) in favor of the alternative ( $p>0.3$ ) at  $\alpha=0.05$ .

Secondary endpoints will utilize the three treatment modality groups:

- #1: treatment stopped due to non-response (per RECIST);
- #2: treatment continued for a full year with good response and good tolerance
- #3: treatment stopped due to poor tolerance in spite of good response;

**Secondary** outcomes will utilize the actual numerical values obtained during the assessment over time to correlate visual function with tumor size (measured at each visit and/or via MRI/CT imaging). The secondary outcome measures will assess each part of the composite visual assessment score to determine changes in vision and lacrimal function following vismodegib treatment.

Histologic characteristics and molecular markers to be studied for the secondary objective include HMW keratin, proliferation markers such as Ki67, hedgehog and Wnt pathway markers. These will be summarized overall, by treatment modalities, and by outcome groups (e.g., Good or Poor Visual or Lacrimal Function). No other subgroup analyses are planned. **Please see page 20, BASIC RESEARCH ARM.**

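### Stable disease needs no minimum time on drug, so a patient who stops early for side effects with an unchanged tumor is filed as a good responder

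*Combined protocol and SAP*

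**What the plan says.** Section 3.1, Response Assessment, item 6 refers to RECIST without naming a version and writes out four classes. Apart from complete disappearance (CR), the thresholds are "Partial response (PR) = at least 30% decrease in largest diameter" and "Progressive disease (PD) = at least 20% increase in largest diameter". What is left over is "Stable disease (SD) = neither PR nor PD". No minimum interval or exposure is attached to SD, and no class is listed for patients who cannot be judged. Item 5 sets the timing: "Assess response by ophthalmic exam at 3 month intervals or at time of early discontinuation of vismodegib". Item 7 then divides patients two ways only: PD on one side, and SD, PR and CR together as responding on the other.

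Under Outcome Assessment, item 9c names CR, PR and SD together as Responders, and item 9e sends patients who stop for side effects they find intolerable to Outcome #3. Section 4.9, Analysis, describes the group with the same number as "treatment stopped due to poor tolerance in spite of good response".

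Item 4a places formal enrollment at the start of vismodegib, and section 4.9 analyses all enrollees, so a patient who stops in the first weeks stays in. Table 16 schedules a response evaluation at early withdrawal.

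On timing, the expanded access study in section 1.3.1.1 reports: "Among patients with laBCC who responded the median and mean times to response were 2.6 months and 3.5 months".

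**The concern.** Read together, these rules give a favourable response label to a patient whose tumor has had too little exposure to show either response or resistance. The label follows from an absence of change over a short time and not from any evidence of drug effect.

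Three pieces of planned work use the label. Section 4.9 summarises histology and markers by treatment modality, that is, by groups #1 to #3. Item 13b matches the pre-treatment specimen with treatment outcome. Secondary objective 3 and the basic research aim in section 3.3 look for features that go with tumor response. If group #3 and the Responder class mix drug-sensitive tumors with untested ones, a marker of sensitivity is diluted. A difference between groups #1 and #3 would also be hard to interpret.

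**Working it through.** **1. The plan's own figure.** For the exact one-sided binomial test with n = 50, p0 = 0.3 and alpha = 0.05, the smallest r with P(X ≥ r | 50, 0.3) ≤ 0.05 is r = 21 (probability 0.0478). Power is P(X ≥ 21 | 50, 0.5) = 0.899, against the stated 90%. The figure reproduces. The test uses the Table 15 score and not the response class, so nothing below changes it.

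**2. The rules applied to one case.** Take a patient who stops for cramps in week 5 with the tumor unchanged.
- Item 4a: enrolled at first dose.
- Item 5: response is assessed at discontinuation.
- Item 6: the decrease is under 30% and the increase under 20%, so the class is SD.
- Item 9c: SD, so Responder.
- Item 9e: stopped for intolerance, so Outcome #3.
- Section 4.9: group #3, described as a good response.

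No step asks how long the patient took the drug.

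**3. Time to response against onset of side effects.** Inputs are Table 7 (locally advanced, 26 responders of 56; median 2.6 months, range 1.0 to 11.0) and Table 8 (median onset 37 days for muscle spasms, 41 days for dysgeusia).
- 2.6 months × 30.44 days = about 79 days.
- By the definition of a median, about 13 of 26 responders took 2.6 months or longer. That is 13/56 = 23% of the evaluable locally advanced patients.
- 37/79 = 0.47 and 41/79 = 0.52, so these side effects typically begin at about half the median time to response, and before the month-3 evaluation.

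**4. The class that is not listed.** Table 7 accounts for its 56 locally advanced patients as 6 CR + 20 PR + 27 SD + 0 PD + 3 unevaluable or missing. Table 3 also keeps such a row (4 of 63). Item 6 has no counterpart.

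**5. How many patients.** Stops for adverse events were 16/71 = 22.5% (Table 5, locally advanced) and 178/500 = 35.6% (STEVIE). Applied to 50 patients: 50 × 0.225 = 11.3 and 50 × 0.356 = 17.8. The documents do not say when these stops occurred, so the share before month 3 is an assumption:

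| Assumed share before month 3 | At 22.5% | At 35.6% |
|---|---|---|
| 10% | 1.1 | 1.8 |
| 25% | 2.8 | 4.5 |
| 50% | 5.6 | 8.9 |

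The range is about 1 to 9 of 50. It is an upper bound under each assumption, because patients already in CR, PR or PD when they stop are classed correctly. Responses were seen from 1.0 month.

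**The case against.** The strongest reply is that little of the planned analysis depends on the label. No response proportion is a planned endpoint. Section 4.9 correlates visual function with tumor size using the numerical values, which no SD cut-off enters. The only example it gives of outcome groups is good or poor visual or lacrimal function. Item 13c identifies group #3 surgical specimens by intolerance, and item 9e states openly that #3 includes SD. RECIST is invoked, and Table 7, itself headed as a RECIST table, carries an unevaluable row, so the investigators may intend to use one. All of this limits the reach of the point. It does not remove it: the summaries by modality, the matching in item 13b and objective 3 remain, and the exposure rule and the extra class are not written in this plan.

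A reader might also infer several stronger things that the documents do not support:
- **That a planned response rate or a formal responder marker test is biased.** Neither is specified.
- **That over half of these labels are wrong, because only 46.4% of locally advanced patients reached CR or PR.** That takes CR or PR as the truth, whereas the plan's Responder means not PD. On that definition PD was 0/56 in Table 7, and 8/63 and 6/63 in Table 3.
- **That up to 13 of 50 are affected.** This uses the 54% stop rate from the Gorlin-syndrome trial in patients with surgically eligible tumors, which is a different population.
- **That untreated tumors fall in SD by default, because placebo-treated tumors changed by -11%.** This is a group mean from the same Gorlin-syndrome trial and does not locate an individual locally advanced tumor between -30% and +20%.
- **That early side effects mean early stops.** Onset is not discontinuation: 63 of the 84 muscle spasm cases in Table 8 were Grade 1 and 2 were Grade 3. Alopecia began at a median of 87 days and weight loss at 175.

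**Conclusion.** The point holds for the secondary groups and the exploratory tissue work, and should be corrected. As written, the rules class any intolerance stop with an unchanged tumor as a good response, however short the exposure, and the background data show that such a label is not evidence of drug sensitivity. The primary endpoint, its test and its power stand.

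The number affected cannot be computed from the documents. About 1 to 9 of 50 is an upper range that rests on two assumptions: that stop rates resemble those in Table 5 and STEVIE, and that 10% to 50% of stops precede month 3. The 2.6-month median comes from 26 responders in one study whose assessment schedule is not given, so observed times may partly reflect visit timing. The good-response wording reaches the early stopper through the shared group number in items 9e and 4.9; section 4.9 does not define it separately.

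**What to change.** Add an analysis rule to section 3.1, items 6 and 9c, and to section 4.9, before any group results are seen. It changes no treatment decision.

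- Let SD count toward Responder status or good response only if the tumor was measured on drug at or after a prespecified minimum time, stated in days. Ninety days is one example. A rule tied to the month-3 visit would not do: its window of one month either side admits a measurement at about 61 days, before the 79-day median. Ninety days is a choice and not a derived threshold, since the mean time to response was 3.5 months and the longest 11.0, so the plan should give its reason.
- Class patients who stop earlier without CR, PR or PD as not evaluable for response.
- Show them as a separate line within group #3, and leave them out of any summary of markers by tumor response.
- If a response proportion is reported, keep them in the denominator as non-responders.

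The cost is a few sentences and no new data. Responder groups become slightly smaller, and any reported response figure slightly less favourable.
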